7.4.5 Management of Potential Hepatobiliary Toxicity

Any subject exhibiting signs/symptoms or laboratory abnormalities suggestive of possible hepatobiliary toxicity should undergo thorough examination and clinical workup as deemed appropriate by the Investigator. Consideration should be given to appropriate imaging studies (e.g., ultrasound of the liver and biliary tree) and potential consultation with a gastroenterologist with specialty training in hepatobiliary diseases.

7.5 Hepatitis C Management

If a subject, tests positive for HCV RNA at screening or develops signs or symptoms of active Hepatitis C Virus, local medical practice is followed at the discretion of the Investigator. Study drug may be continued without interruption. Should the Investigator decide to initiate Hepatitis C treatment the investigator confirms that no drug-drug interactions are expected. Subjects should return to the clinic for scheduled or unscheduled follow up visits according to local medical practice for laboratory evaluations.

7.6 Special Situations Reports

7.6.1 Definitions of Special Situations

Special situation reports include all reports of medication error, abuse, misuse, overdose, reports of adverse events associated with product complaints, reports of adverse reactions in infants following exposure from breastfeeding, occupational exposure with an adverse event, and pregnancy reports regardless of an associated AE.

Medication error is any unintentional error in the prescribing, dispensing, or administration of a medicinal product while in the control of the health care provider, subject or consumer.

Abuse is defined as persistent or sporadic intentional excessive use of a medicinal product by a subject.

Misuse is defined as any intentional and inappropriate use of a medicinal product that is not in accordance with the protocol instructions or the local prescribing information.

An overdose is defined as an accidental or intentional administration of a quantity of a medicinal product given per administration or cumulatively which is above the maximum recommended dose per protocol or in the product labelling (as it applies to the daily dose of the subject in question). In cases of a discrepancy in drug accountability, overdose will be established only when it is clear that the subject has taken the excess dose(s). Overdose cannot be established when the subject cannot account for the discrepancy except in cases in which the investigator has reason to suspect that the subject has taken the additional dose(s).

Product complaint is defined as complaints arising from potential deviations in the manufacture, packaging, or distribution of the medicinal product.

Occupational exposure is defined as exposure to a medicinal product as a result of one's professional or non-professional occupation.

7.6.2 Instructions for Reporting Special Situations

7.6.2.1 Instructions for Reporting Pregnancies

The Investigator will report pregnancies in subjects that are identified after initiation of the study drug and throughout the study to Gilead.

The subject should receive appropriate monitoring and care until the conclusion of the pregnancy.

The pregnancy itself is not considered an AE nor is an induced elective abortion to terminate a pregnancy without medical reasons.

Protocol IN-US-380-4543

Any premature termination of pregnancy (e.g., spontaneous abortion, induced therapeutic abortion due to complications or other medical reasons) must be reported within 24 hours as an SAE. The underlying medical reason for this procedure should be recorded as the AE term.

A spontaneous abortion is always considered to be an SAE and will be reported as described in section 7.3. Furthermore, any SAE occurring as an adverse pregnancy outcome post study will be reported to Gilead.

The outcome should be reported to Gilead via email or fax to:

Email: Safety [contact]

[contact]

7.6.2.2 Reporting Other Special Situations

Any inappropriate use of concomitant medications prohibited by this protocol should not be reported as "misuse," but may be more appropriately documented as a protocol deviation.

Refer to Section 7.3 for full instructions on the mechanism of special situation reporting.

All clinical sequelae in relation to these special situation reports will be reported as AEs or SAEs at the same time using the AE EMR and/or the SAE report form. Details of the symptoms and signs, clinical management, and outcome will be reported, when available.

8. STATISTICAL CONSIDERATIONS

8.1 Analysis

The efficacy analysis endpoints are as follows:

8.1.1 Primary Endpoint

The primary efficacy endpoint is the proportion of subjects that have HIV-1 RNA ≥ 50 copies/mL at week 48, as defined by the FDA snapshot analysis.

8.1.2 Secondary Endpoints

- The proportion of subjects that have HIV-1 RNA <50 copies/mL at Week 48, as defined by the FDA snapshot analysis.
- 2. The change in serum creatinine from Day 1 to Week 48
- The change in CD4 cell count at Day 1 to Week 48
- 4. The change in lipid parameters at Day 1 to Week 48
- 5. The change in responses to the PRO at Day 1, Week 4, 12, and 48

8.2 Analysis Conventions

8.2.1 Analysis Sets

8.2.2 Full Analysis Set

The primary analysis set for efficacy analyses is defined as FAS, which will include all subjects who have received at least 1 dose of study drug. Subjects who do not receive at least 1 dose of study drug will be excluded from all analysis.

8.2.3 Safety

The primary analysis set for safety analysis is defined as safety analysis set, which will include all subjects who have received at least 1 dose of study drug. All the data collected up to 30 days after subjects permanently discontinue their study drug will be included in the safety summaries, unless specified otherwise.

Protocol IN-US-380-4543

8.3 Data Handling Conventions

For analysis purposes, laboratory data that are continuous in nature but are ≤ the lower limit or ≥ the upper limit of quantitation will be inputted to the value of the lower limit minus 1 or upper limit plus 1 significant digit, respectively (e.g., If HIV-1 RNA results of 'No HIV-1 RNA detected' and '≤ 50 copies/mL HIV-1 RNA detected' will be inputted as 49 copies/mL).

Missing data can have an impact upon the interpretation of the trial data. In general, values for missing data from the specified visit will not be inputted. However, a missing pre-treatment laboratory result would be treated as normal (i.e. No toxicity grade) for the laboratory abnormality summary.

All available data for subjects that do not complete the study will be included in data listings.

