2. STUDY OBJECTIVES

2.1. The primary objective of the study is:

To evaluate the proportion of participants with virologic failure determined by HIV-1 RNA ≥ 50 copies/mL at week 48 in virologically suppressed patients with HIV-1 infection switching from ATRIPLA® to BIKTARVY®.

2.2. The secondary objectives of the study are:

- To determine the safety of switching from ATRIPLA® to BIKTARV®Y in virologically suppressed
 patients with HIV-1 infection as determined by the proportion of participants with virologic failure, a
 rise in serum creatinine values, a change in lipid parameters, and change in CD4 cell count from
 baseline.
- To determine the efficacy of switching from ATRIPLA® to BIKTARVY® in virologically suppressed
 patients with HIV-1 infection as determined by the proportion of participants with HIV-1 RNA < 50
 copies/MI.
- To evaluate tolerability, durability of BIKTARVY® in virologically suppressed patients with the aid of 2 Patient Reported Outcomes (PRO) questionnaires (see appendix 3).

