3. STUDY ENDPOINTS

3.1. Primary Endpoint

• The primary efficacy endpoint is the proportion of subjects that have HIV-1 RNA ≥ 50 copies/mL at week 48, as defined by the FDA snapshot analysis.

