8.5 Efficacy Analysis

8.5.1 Primary Analysis

The primary analysis will consist of a descriptive analysis of switching from EFV/TDF/FTC to BIC/FTC/TAF with respect to the proportion of subjects with HIV-1 RNA ≥ 50 copies/mL at Week 48 as defined by the US FDA-defined snapshot algorithm. The primary analysis of the efficacy endpoint will be based on the FAS.

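### Section 8.3 recodes HIV-1 RNA of ≤ 50 copies/mL to 49, although the primary endpoint counts a result of 50 as failure

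*Combined protocol and SAP*

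**What the plan says.** Section 3.1 defines the primary endpoint as "the proportion of subjects that have HIV-1 RNA ≥ 50 copies/mL at week 48, as defined by the FDA snapshot analysis". Sections 8.1.1 and 8.5.1 repeat that threshold; the primary analysis is described as descriptive, "with respect to the proportion of subjects with HIV-1 RNA ≥ 50 copies/mL at Week 48". The snapshot algorithm in Section 8.5.1.1 splits subjects with a Week 48 result into < 50 and ≥ 50. The first secondary endpoint (Sections 3.2 and 8.1.2) is the proportion below 50. In all of these places a value of 50 is a failure.

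Section 8.3 then gives a general imputation rule for analysis: "laboratory data that are continuous in nature but are ≤ the lower limit or ≥ the upper limit of quantitation will be inputted", at the lower end to the limit minus 1. Its worked example concerns HIV-1 RNA. Both an undetected result and the category "≤ 50 copies/mL HIV-1 RNA detected' will be inputted as 49 copies/mL".

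On a related point of wording, objective 2.1 speaks of "virologic failure determined by HIV-1 RNA ≥ 50 copies/mL at week 48", and Section 6.2.5 gives a wider definition that adds rebound and RNA ≥ 50 at discontinuation. Objective 2.2 assesses safety partly "as determined by the proportion of participants with virologic failure", without saying which of the two is meant.

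**The concern.** One reported value, 50 copies/mL, satisfies both the failure definition and the recoding rule. A programmer who follows Section 8.5.1.1 on the reported value counts it as failure. One who applies Section 8.3 first sets it to 49 and counts it as success. The example is about the primary endpoint variable, and Section 8.3 exempts no endpoint.

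The study is a single cohort of about 100 subjects with a descriptive primary analysis. If failures are few, moving one subject changes the headline figure visibly, and the move goes in the favourable direction.

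**Working it through.** **Inputs.** Failure threshold ≥ 50 (Sections 3.1, 8.1.1, 8.5.1, 8.5.1.1). Success threshold < 50 (Sections 3.2, 8.1.2). Recoding rule: a value at or below the lower limit L becomes L − 1 (Section 8.3). Sample size about 100 (Sections 4.3 and 8.8). No section states the assay's quantitation limit.

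**Step 1: reproduce the plan's figure.** With L = 50, L − 1 = 49, which is the value in the Section 8.3 example. The example therefore implies a limit of 50.

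**Step 2: apply the rule with L = 50 and classify.** The last column replaces ≤ by strict < in the rule.

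| Reported value | Category as reported | Value after 8.3 | Category after 8.3 | Category under strict < |
|---|---|---|---|---|
| 20 | < 50 | 49 | < 50 | < 50 |
| 49 | < 50 | 49 | < 50 | < 50 |
| 50 | ≥ 50 | 49 | < 50 | ≥ 50 |
| 51 | ≥ 50 | 51 | ≥ 50 | ≥ 50 |

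Only the value 50 changes category under the plan's wording. Strict wording restores it and leaves the other three rows alone.

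**Step 3: vary the limit.** The limits 20 and 40 are assumptions, for comparison.

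- L = 20: 50 is above the limit, stays 50, failure.
- L = 40: 50 is above the limit, stays 50, failure.
- L = 50: 50 is at the limit, becomes 49, success.

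The conflict affects the endpoint only at the limit that the example implies.

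**Step 4: size per affected subject.** 1/100 = 1.0 percentage point off the ≥ 50 proportion, and 1.0 point added to the < 50 proportion. As an illustration with assumed counts, 2/100 = 2% (exact 95% interval 0.24% to 7.04%) would be reported as 1/100 = 1% (0.03% to 5.45%). The intervals are added here for scale; the plan does not specify any.

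**The case against.** The strongest reply is that the rule may never touch the endpoint. Section 8.5.1.1 classifies subjects by their last on-treatment laboratory result, which can be read as the result the laboratory reported. Section 8.3 is about continuous data, and its example names report categories, so it may have been meant only for summaries of continuous values. If so, or if the assay limit is below 50, no subject is misclassified. This stands as a limit on the consequence. It does not remove the contradiction: Section 8.3 applies to analysis in general, and Section 8.5.1.1 does not say whether reported or imputed values are used.

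A second reply is that the symbol is a slip. That is less likely, because the general rule in the same sentence also includes the limit itself, at both the lower and the upper end. Slip or not, the text needs the same correction.

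On virologic failure, a reader might infer that the wider Section 6.2.5 outcome is a promised safety measure left without analysis, with off-drug values appearing nowhere but in listings, since Section 8.3 says "All available data for subjects that do not complete the study will be included in data listings". The documents do not support that. Sections 8.2.3 and 8.6 bring safety data up to 30 days after the last dose into the summaries. Section 8.6.3 covers selected laboratory data, so a dedicated RNA table is not guaranteed, but confinement to listings is not what the plan says. The natural reading of objective 2.2 also carries over the meaning in objective 2.1 directly above it, which Section 8.5.1 already analyses. What remains is a missing cross-reference: a confirmed rebound that is below 50 again at Week 48 is failure under Section 6.2.5 but falls in the < 50 snapshot category.

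**Conclusion.** The concern holds as a minor error of wording in an analysis rule. Section 8.3, as written, contradicts the primary endpoint, the snapshot algorithm and the first secondary endpoint at the value 50.

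The effect on results is conditional. It needs a quantitation limit of 50 and classification on imputed values; the first is implied only by the example and the second is left open. If both hold, the shift is 1 percentage point per exact-50 result at 100 subjects, always towards fewer failures. If either fails, the shift is zero. A reader might infer that the primary result will be biased; the documents do not support that, because they give neither the assay limit nor any basis for expecting exact-50 results.

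The ambiguity in objective 2.2 is an editorial matter and calls for no additional analysis.

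**What to change.** In Section 8.3, restrict imputation to undetected HIV-1 RNA and to results reported as strictly below the lower or strictly above the upper limit of quantitation. Change the example from ≤ 50 to < 50 copies/mL, and state that a reported 50 is kept as 50. For any assay limit of 50 or lower, a result of 50 is then a failure whether the snapshot uses reported or imputed values.

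Optionally, add a cross-reference in objective 2.2 saying whether virologic failure has the objective 2.1 or the Section 6.2.5 meaning.

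Both are text edits. They need no new data, table or visit, and they leave the primary endpoint and the snapshot rule as they are. The Section 8.3 edit should be made before the Week 48 analysis is run.

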8.4 Demographic Data and Baseline Characteristics

Demographic and baseline characteristics will be summarized using standard descriptive methods including sample size, mean, SD, median, minimum, and Maximum for continuous variables and frequency and percentages for categorical variables.

Demographic data will include sex, race, ethnicity, and age.

Baseline characteristics will include body weight, height, creatinine, lipid parameters and CD4 at baseline.

8.5 Efficacy Analysis

8.5.1 Primary Analysis

The primary analysis will consist of a descriptive analysis of switching from EFV/TDF/FTC to BIC/FTC/TAF with respect to the proportion of subjects with HIV-1 RNA ≥ 50 copies/mL at Week 48 as defined by the US FDA-defined snapshot algorithm. The primary analysis of the efficacy endpoint will be based on the FAS.

8.5.1.1 US FDA-defined Snapshot Algorithm

All HIV-1 RNA data collected on-treatment (i.e. including data collected up to 1 day after the last dose date of the study drug) will be used in the snapshot algorithm. Virologic outcome will be defined as the following categories:

- HIV-1 RNA < 50 copies/mL: subjects who meet this criteria by result of the last available ontreatment laboratory result in the Week 48 analysis window
- HIV-1 RNA ≥ 50 copies/mL: subjects who meet this criteria by result of the last available ontreatment laboratory result in the Week 48 analysis window or do not have laboratory results in the Week 48 window and who discontinue study drug either:
 - due to lack of efficacy or
 - for reason other than lack of efficacy and have the last available on-treatment HIV-1 RNA ≥ 50 copies/mL
- No virologic Data in the Week 48 Analysis Window: subjects who do not have on-treatment HIV-1 RNA data in the Week 48 window because
 - Discontinuation of the study drug for reason other than lack of efficacy and have the last available on-treatment HIV-1 RNA < 50 copies/mL or
 - Missing data during the Week 48 window but remain on study drug

8.5.1.2 Analysis of Primary Efficacy Endpoint

The evaluation will be based on the proportion of subjects with HIV-1 RNA ≥ 50 copies/mL at Week 48.

8.5.2 Secondary Analyses

The proportion of subjects with HIV-1 RNA <50 copies/mL at Week 48 as defined by the US FDA-defined snapshot algorithm will also be summarized.

The Change from baseline in CD4+ cell count at Week 48 will be summarized by treatment using descriptive statistics.

8.6 Safety Analysis

All safety analyses will be performed using the full analysis set.

All safety a data collected on or after the date of the study drug was first administered up to the date of the last dose of study drug plus 30 days, unless specified otherwise, will be summarized for subjects in the safety analysis set.

Data for the pretreatment period and the period past the date of last dose of study drug plus 30 days will be included in data listings for all enrolled subjects.

8.6.1 Extent of Exposure

Duration of exposure to study drug will be expressed as the number of weeks between the first and last dose of the study drug, inclusive, regardless of temporary interruptions in study drug administration and summarized by treatment.

8.6.2 Adverse Events

Clinical and laboratory adverse effects will be coded using the definitions detailed in Appendix 2 and recorded in the study database.

Summaries (number and percentages of subjects) of treatment-emergent adverse events (by SOC, HLT [if applicable], and PT) will be provided by treatment. Additional summaries will include summaries for adverse events by grade, Investigator's assessment of relationship to study drug and effect on study drug dosing.

On an ongoing basis adverse events will be reviewed for event that might meet the definition of Stage 3 Opportunistic Illnesses in HIV that are indicative of an AIDS-Defining Diagnosis. The Principal Investigator will review the possible Stage 3 events and approve the events that meet the definition. Those events that do meet the Stage 3 Opportunistic Illnesses definition of an AIDS-Defining Diagnosis will be listed in Appendix 2.

8.6.3 Laboratory Evaluations

Selected laboratory data (using conventional units) will be summarized using only observed data. Absolute values and changes from baseline at all scheduled visits will be summarized.

Graded laboratory abnormalities will be defined using the Grading of Laboratory Abnormalities in Appendix 2

Incidence of treatment-emergent laboratory abnormalities, defined as values that increase at least 1 toxicity grade from baseline at any time post baseline up to and including the date of last dose of study drug plus 30 days will be summarized. If baseline data are missing, then any graded abnormality (i.e., at least a Grade1) will be considered treatment emergent. The maximum post baseline toxicity grade will be summarized by laboratory parameter.

Laboratory abnormalities that occur before the first dose of study drug or after the last dose of study drug plus 30 days will be included in a data listing.

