5. STUDY DATA

Demographic summaries will include sex, race/ethnicity, age, prior antiviral therapies and (if available) pertinent prior mutations. Data relevant to endpoint evaluation includes subject HAART regimen, viral load (VL), CD4 T-cell count, fasting lipid panel, serum creatinine, PRO, at initial screening, weeks 4, 8, 12, 24, 36 and 48.

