6.2.2.2 Day 1/Baseline Visit

The Investigator must have confirmed eligibility before proceeding with the Day 1 Visit.

The subject must complete prior to being administered the study drug:

- Subject will read PRO questionnaires (appendix 3) and write/mark answers directly onto questionnaire.
- Review/record SAE/AE's and changes in concomitant medications
- Obtain measurements of blood pressure, pulse, temperature, height and weight
- Complete physical exam (genital/rectal exam, if clinically indicated)
- Obtain blood and urine samples as described in section 6.2.9
- Dispense study drug
- Observe first dose administration of study drug.
- Subjects will be counseled regarding the importance of adherence and taking the study medication at the same time each day.
- Record all AE/SAE's to any protocol mandated procedures

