6.2.2.4 Early Study Drug Discontinuation Assessment

If the subject discontinues the study drug prior to the Week 48 Visit, the subject will be asked to return to the clinic within 5 days of stopping study drug for the Early Study Drug Discontinuation Visit. Every attempt should be made to keep the subject in the study and continue to perform the required follow ups and procedures through to the Week 48 Visit (see Section 6.2.2.3). If this is not acceptable to the subject or investigator, the subject may be withdrawn from the study.

If the subject discontinues the study drug and without notifying the Investigator within 5 days, the subject may be withdrawn from the study, at the Investigator's discretion.

At the Early Study Discontinuation Visit, any evaluations showing abnormal results indicating that there is a possible or probable causal relationship with the study drug will be repeated weekly (or as often as deemed prudent by the Investigator) until the abnormality is resolved/returns to baseline (based on Day 1 Visit) or is otherwise explained.

The following will be completed:

- Review/record of SAE/AE's and changes in concomitant medications
- Obtain measurements of blood pressure, pulse, temperature, height and weight
- Complete or symptom directed physical exam, as clinically indicated
- Obtain blood and urine samples as described in section 6.2.4.1
- Document accountability for all study drugs.

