APPENDIX 1. SCHEDULE OF STUDY VISITS

	SCREENING VISIT	Day 1 a	WEEK 4 ^a	WEEK 8 a	WEEK 12 ^b	WEEK 24 ^b	WEEK 36 ^b	WEEK 48 °	EARLY DISCONTINUATION
Informed Consent	X								
Patient Questionnaires		X	X		X			X	X
Height	X								
Weight	X	X	X	X	X	X	X	X	X
Vital Signs	X	X	X	X	X	X	X	X	X
Complete Medical History & Physical Exam	X								
Concomitant Medication Review	X	X	X	X	X	X	X	X	X
Assess for Adverse Experiences			X	X	X	X	X	X	X
Abbreviated History & Physical Exam		Х	Х	Х	Х	Х	Х		
Hematology	X	X	X	X	X	X	X	X	X
Chemistry	X	X	X	X	X	X	X	X	X
CD4 Profile	X	X	X	X	X	X	X	X	X
HIV- RNA Quantitative	X	X	X	X	X	X	X	X	X
Fasting Lipid Profile		X			X	Х	X	X	X
Plasma and serum Storage Sample		X	X	X	X	X	X	X	X
Urinalysis	X		X	X	X	Х	Х	X	X
Hepatitis B Surface antigen, Surface antibody, and Core Antibody ^d	X								X
Hepatitis C antibody e	Х								X
Plasma Hepatitis B viral load ^f	X		Х	Х	Х	Х	Х	Х	X
Females of childbearing potential: Pregnancy Test (Urine)	Х	X	Х	X	X	Х	Х	Х	Х
Dispensing or Administration of Study Drug		Х	Х	Х	Х	Х	Х		
Counting of Returned Study Drug			Х	X	X	Х	Х	Х	Х

a ±2 days

b ±6 days

^{±6} weeks

If Hepatitis B Surface antigen positive or if Ag/Ab negative with Core antibody positive: plasma qualitative and quantitative HBV DNA, Hepatitis B virus e-antigen and antibody

e If Hepatitis C antibody positive, HCV RNA will be performed

f If Hepatitis B coinfected

Page 29 of 38

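### Appendix 1 leaves Day 1 urinalysis blank and laboratory baseline is never defined, so urine abnormalities already present at Screening could be counted as treatment-emergent

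*Combined protocol and SAP*

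**What the plan says.** **The rule.** Section 8.6.3 counts laboratory abnormalities as treatment-emergent when they are "defined as values that increase at least 1 toxicity grade from baseline at any time post baseline". For subjects without a baseline it adds: "If baseline data are missing, then any graded abnormality (i.e., at least a Grade1) will be considered treatment emergent". Section 8.3 has a companion rule for the abnormality summary: "a missing pre-treatment laboratory result would be treated as normal".

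**The baseline.** Section 6.2.2.2 is headed "Day 1/Baseline Visit". Section 6.2.2.4 follows abnormal results until the value "returns to baseline (based on Day 1 Visit"). Section 8.1.2 restates the change-from-baseline endpoints of 3.2 as changes from Day 1. Section 8 contains no definition of baseline for laboratory data. Section 5 lists endpoint data "at initial screening, weeks 4, 8, 12, 24, 36 and 48", without Day 1, but it does not mention urinalysis.

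**The schedule.** The Appendix 1 urinalysis row is marked at Screening, blank at Day 1, and marked at Weeks 4, 8, 12, 24, 36 and 48 and at Early Discontinuation. The urine pregnancy test, by contrast, is marked at Day 1. Section 6.2.2.2 lists blood and urine sampling among the Day 1 procedures but refers to Section 6.2.9, which does not exist. Section 6.2.4.2 lists urinalysis among the urine tests without restricting it to particular visits. Section 6.2.4 cites both Section 6.2 and Appendix 1 and gives neither precedence.

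**The grading.** Appendix 2 grades hematuria, proteinuria and glycosuria from 1 to 3.

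**The concern.** The missing-baseline rule suits an occasional lost sample. Here it may apply to everyone: under Appendix 1 no subject has a Day 1 urinalysis, so if baseline is strictly the Day 1 value the rule becomes the only rule for three graded parameters. A subject with 1+ proteinuria on ATRIPLA at Screening and the same 1+ at Week 12 would be tabulated as having developed it on BIKTARVY.

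Reduced renal risk after leaving TDF is a stated reason for the switch (1.1) and a stated benefit (4.6), so these urine rows will be read with interest. The study is a single cohort, so no control arm would show the same artefact. Screening results would appear only in a listing of pre-treatment data (8.6, 8.6.3), not in the incidence summary.

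**Working it through.** The plan states no figure on this point, so there is none to reproduce.

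**Step 1. Conditions.** The miscount needs both of these:
- Sites follow Appendix 1 and do no urinalysis at Day 1.
- Baseline means the Day 1 value only, with no fallback to Screening.

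**Step 2. Do the two missing-data rules differ?** Under 8.6.3, a missing baseline makes any grade of 1 or more emergent. Under 8.3, a missing pre-treatment result counts as grade 0, so any later grade of 1 or more is a rise of at least one grade and again emergent. The outcome is the same, so 8.3 gives no protection once the baseline is treated as missing.

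**Step 3. Which subjects are misclassified?** Cross the Screening grade (0-3) with the post-dose grade (0-3), giving 16 pairs. With a pre-dose baseline, a value is emergent if post ≥ Screening + 1. With baseline missing, it is emergent if post ≥ 1.

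| Screening grade | Emergent post grades, pre-dose baseline used | Emergent post grades, baseline missing | Post grades that differ |
|---|---|---|---|
| 0 | 1, 2, 3 | 1, 2, 3 | none |
| 1 | 2, 3 | 1, 2, 3 | 1 |
| 2 | 3 | 1, 2, 3 | 1, 2 |
| 3 | none | 1, 2, 3 | 1, 2, 3 |

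Six of the 16 pairs differ (1/1, 2/1, 2/2, 3/1, 3/2, 3/3). All are abnormalities that were present at Screening and stayed stable or improved. A normal Screening urinalysis gives the same classification under either reading.

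**Step 4. Size, on assumed inputs.** The documents give no prevalence. Assume that:
- a fraction p of subjects (5-20%) has a pre-existing, non-worsening abnormality;
- it shows in any one sample with probability q (0.3-0.8), independently between samples and at the same grade whenever it shows;
- there are 6 scheduled post-dose samples (Weeks 4 to 48).

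A false case that a Screening baseline would remove must be positive at Screening (probability q) and positive at least once afterward (probability 1-(1-q)^6):

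excess per 100 = 100 × p × q × [1-(1-q)^6]

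| q | 1-(1-q)^6 | p = 5% | p = 20% |
|---|---|---|---|
| 0.3 | 0.882 | 5 × 0.3 × 0.882 = 1.3 | 20 × 0.3 × 0.882 = 5.3 |
| 0.5 | 0.984 | 5 × 0.5 × 0.984 = 2.5 | 20 × 0.5 × 0.984 = 9.8 |
| 0.8 | 1.000 | 5 × 0.8 × 1.000 = 4.0 | 20 × 0.8 × 1.000 = 16.0 |

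The range is about 1-16 per 100 subjects per parameter, and the planned sample is about 100.

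**The case against.** **The Day 1 urinalysis may not be missing at all.** Section 6.2.2.2 calls for urine before the first dose, and 6.2.4.2 includes urinalysis without visit limits. The 6.2.9 pointer also appears in the Screening text, where Appendix 1 does mark urinalysis, so it looks like a stale reference to 6.2.4. Appendix 1 also leaves height and adverse event assessment blank at Day 1, although 6.2.2.2 requires both, so the urinalysis blank may be clerical. This stands in part: the documents conflict, and they do not show that the sample will be absent. But they do not show that it will be taken either. The Day 1 urine could be the pregnancy test alone, which is the only urine test Appendix 1 marks at that visit.

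**A Day 1-only baseline is inferred.** Section 8.1.2 names Day 1 only for creatinine, CD4, lipids and the PROs, 6.2.2.4 concerns follow-up of abnormal results, and 8.3 says pre-treatment, which could include Screening. On that reading the problem disappears. It is a permissible reading, but nothing instructs a programmer to adopt it, and 8.6.3 says baseline.

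**Stronger claims a reader might infer.**
- *Every graded urine value will be falsely emergent.* Step 3 shows otherwise: only non-worsening abnormalities already present at Screening are miscounted, and only if both conditions hold.
- *The size is prevalence × [1-(1-q)^6], about 4-20 per 100* (5 × 0.882 = 4.4 to 20 × 1.000 = 20.0). That counts subjects whose Screening sample was negative; a Screening baseline would still call them emergent.
- *The study's renal conclusion is reversed.* The named renal endpoint is serum creatinine, which falls under the chemistry profile that Appendix 1 schedules at both Screening and Day 1. A descriptive incidence table in one cohort does not assign cause.

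**Conclusion.** The point holds as a conditional one. The schedule and the text disagree on Day 1 urinalysis, and laboratory baseline is undefined. If Appendix 1 is followed and baseline is Day 1 only, the urine baseline is missing for all subjects, and 8.6.3 (equally 8.3) overstates treatment-emergent hematuria, proteinuria and glycosuria by counting stable or improved pre-existing abnormalities.

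The avoidable excess is about 1-16 per 100 subjects per parameter. That range rests on the assumed prevalence, the assumed chance of showing at each visit, and independence between visits; none of these comes from the documents. Whatever the inputs, the excess cannot exceed the number of subjects positive at Screening.

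The effect is confined to the laboratory abnormality summary. No primary or secondary endpoint is affected. This is a free improvement: worth making because it costs nothing, not because the trial's main results depend on it.

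**What to change.** 1. In 8.3 and 8.6.3, define laboratory baseline for every parameter as the last non-missing value on or before the first dose: Day 1 if available, otherwise Screening.
2. Apply the missing-baseline rule only when neither value exists, and use the same term in both sections in place of baseline in one and pre-treatment in the other.
3. Reconcile 6.2.2.2, 6.2.4.2 and the Appendix 1 urinalysis row so that they agree on whether urinalysis is done at Day 1, and correct the reference to Section 6.2.9.

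The cost is one definition, one programming rule and a correction to the text. Screening urinalysis is already scheduled, within 30 days before Day 1, so the definition works whichever way the schedule is resolved and needs no new procedure.
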